11.2.5 Reporting of Serious Adverse Events and Serious Adverse Device Effects

When reporting adverse events, all pertinent data protection legislation must be adhered to.

The serious adverse event report should contain the following information*:

1. Study identifier (EudraCT number if applicable)
2. Participant's unique study number
3. Date of birth
4. Event description
5. Start date of event
6. Laboratory tests used and medical interventions used to treat the SAE
7. Planned actions relating to the event, including whether the study device was discontinued
8. Statement on the patient's current state of health
9. Reason for seriousness (i.e. death, life threatening, hospitalisation, disability/incapacity or other)
10. Evaluation of causality (including grade of relatedness) with the following (more than one may apply):
 - a. the investigational treatment/medical device
 - b. the clinical study/a study specific procedure
 - c. other: e. g. concomitant treatment, underlying disease
11. Reporter's name, date and signature

*In the case of incomplete information at the time of initial reporting, all appropriate information should be provided as soon as this becomes available.

The relationship of the SAE to the investigational treatment / medical device should be assessed by the investigator at site, as should the anticipated or unanticipated nature of any SAEs and SADEs. All SAEs whether or not deemed investigational method/device related and whether anticipated or unanticipated must be reported to the Sponsor by email or fax within 24 hours (one working day) of the Investigator learning of its occurrence.

UK specific reporting instructions:

SAEs should be reported to:

[name]
Cambridge University Hospitals
NHS Foundation Trust
Box 277, Addenbrooke's Hospital
[name], UK
[contact]
[contact]
E-mail: r&[contact]

A written report must follow within five working days and is to include a full description of the event and sequelae, in the format detailed on the Serious Adverse Event reporting form. If applicable, the Sponsor will notify the competent authority of all Serious Adverse Events in line with pertinent legal requirements.

The Investigator will notify the Research Ethics Committee (REC) in UK of all Serious Adverse Events in line with pertinent legal requirements. The Investigator will inform the Sponsor about all reports sent to the reporting organisation including follow-up information and answers by the reporting organisation. The local investigator is responsible for informing other site principal investigators and the CI of all SAEs.

The regulatory authority (MHRA) will be notified of all SAEs as soon as possible within ten days of the event occurring during the study. The main REC/IRB will be notified of all unexpected and related SAEs within 15 days of the occurrence of the event.

USA specific reporting instructions:

SAEs should be reported to:

[name]
Jaeb Center for Health Research
[name], USA
[contact]
APP [contact]
E-mail: [contact]

It is the responsibility of the local investigator to follow the SAE and SADE reporting requirements stipulated by the Investigational Center's reviewing IRB and the Sponsor.

11.2.6 Recording and Reporting of Device Deficiencies

All device deficiencies will be documented throughout the study. The investigator at each site will be responsible for managing all device deficiencies and determine and document in writing whether they could have led to a serious adverse device effect.

All device deficiencies that might have led to a serious adverse device effect(s) if: suitable action had not been taken; intervention had not been made; or if circumstances had been less fortunate, must be reported to the Sponsor as for SAEs/SADEs.

11.2.7 Healthcare Arrangements and Compensation for Adverse Events

Healthcare arrangements for subjects who suffer an adverse event as a result of participating in the study may include advice from clinical members of the study team or the patient's treating diabetes team, or use of emergency health services.

If an adverse event occurs, there are no special compensation arrangements unless this was due to the negligence of one of the clinical investigators or due to harm resulting from study protocol design. In this case subjects may have grounds for legal action for compensation. The normal national complaints mechanism will be available. In addition, any harm arising due to study design (both negligent and non-negligent) will be covered under Sponsor's insurance policy as applicable.

11.3 Anticipated Adverse Events, Risks and Benefits

11.3.1 Risks and anticipated adverse events

Known risks represent hazardous situations which may result in anticipated adverse events. In the following text, where appropriate, the term "risk" and "anticipated adverse events" are used interchangeably without affecting meaning.

11.3.2 Hypoglycaemia and Hyperglycaemia

Subjects with type 1 diabetes have a pre-existing risk for hypoglycaemia and hyperglycaemia. Potential risks are:

- Risk of mild to moderate hypoglycaemia and associated symptoms such as sweating, trembling, difficulty thinking and dizziness. There is also a rare risk of severe hypoglycaemia when conscious level is altered, needing help from a third party to correct the hypoglycaemia. These risks are pre-existent in any patient with type 1 diabetes and the study objective is to develop systems to minimise these risks
- Risk of possible mild to moderate hyperglycaemia similar to the risk that a subject with type 1 diabetic experiences on a daily basis
- Risk of hyperglycaemia leading to diabetic ketoacidosis (DKA). This risk is pre-existent in any patient with type 1 diabetes.

11.3.3 Blood Sampling

Subjects will be required to have three blood tests (venepuncture) during the whole study. Venepuncture is required annually as part of the annual review for people with diabetes, and in some places venepuncture is required every 3 to 6 months for assessment of HbA1c. Potential risks include:

- Slight discomfort or bruising at the site (common)
- Excess bleeding at the site (unlikely)
- Infection at the site (rare)

Local anaesthetic cream or spray may be used to minimise the discomfort.

11.3.4 Finger-prick Blood Glucose Measurements

Finger-prick tests may produce pain and/or bruising at the site.

11.3.5 Insulin Pump Therapy

Patients participating in this study are already using an insulin pump. Potential risks associated with insulin pump therapy include:

- Slight discomfort at the time of insertion of the insulin delivery cannula (common)
- Slight bruising at the site of insertion (common)
- Bleeding at insertion site (rare)
- Infection at the site of insertion (rare)
- Allergy to the insulin delivery cannula or adhesive (rare)
- Infusion set and cannula occlusions (rare)
- Insulin pump malfunction and mechanical problems (rare)
- Allergy to insulin (very rare)
- Lipodystrophy / lipoatrophy (very rare)

11.3.6 Continuous Glucose Monitoring

Potential risks associated with CGM:

- Slight discomfort at the time of insertion of CGM (common)
- Slight bruising at the site of insertion (unlikely)
- Bleeding at insertion site (rare)
- Infection at the site of insertion (rare)
- Allergic reaction to the CGM sensor material (rare)

If a skin reaction is classified as severe (the observation is noticeable and bothersome to subject and may indicate infection or risk of infection or potentially life-threatening allergic reaction), an adverse event form will be completed.

11.3.7 Questionnaires

As part of the study, subjects will complete semi-structured interviews and questionnaires which include questions about their private attitudes, feelings and behaviour related to diabetes. It is possible that some people may find these questionnaires to be mildly upsetting. Similar questionnaires have been used in previous research and these reactions are uncommon.

11.3.8 Risk Analysis and Residual Risk Associated with the Investigational Device

A detailed risk analysis for the closed loop system was conducted, according to Cambridge University Hospitals NHS Foundation Trust's standard Risk Assessment Tool. The risk analysis is presented in a separate risk analysis report

The hazard analysis has led to two hazardous situations in which the residual risk identified exceed a predefined score after all practicable control measures have been applied. Risk/benefit analyses concerning these hazardous situations have been conducted by experienced and knowledgeable multidisciplinary members of the research team.

The risks/benefit analysis concluded that day and night closed loop is expected to reduce substantially but not to eliminate the risk of plasma glucose levels below 2.0 mmol/l (36mg/dl). This is supported by clinical data recorded over more than 100 nights at the clinical research facility, by simulations, and is further enhanced by the requirement for a calibration check to be performed each night before closed loop is initiated.

11.4 Benefits

It is expected that day and night closed loop system in combination pump suspend feature or sensor augmented pump therapy alone may have an important role in the management of diabetes. Therefore, the results of this study are likely to be beneficial for subjects with diabetes.

It is possible that subjects will not directly benefit from being a part of this study. However, it is also possible that the blood sugar information from the CGM devices along with the information about insulin dosing during day and night closed loop will be useful for subjects' diabetes self-management.

11.5 Data Safety Monitoring Board (DSMB)

An independent Data Safety Monitoring Board (DSMB) will be informed of all serious adverse events and any unanticipated adverse device effects that occur during the study and will review compiled adverse event data at periodic intervals.

12 Methods and Assessments

12.1 Procedures

12.1.1 Height and Weight

These will be recorded at the study initiation visit at screening. Weight will be also measured at the start and the end the study interventions. Height will be measured in centimetres using a calibrated stadiometer. Weight will be measured in kilograms using a calibrated electronic scale.

12.1.2 Continuous Subcutaneous Glucose Monitoring

At least 12 days of study CGM data will be collected prior to the beginning of the study with the aim of gaining knowledge of the specific subject's glucose control characteristics at screening and assessing compliance before the beginning of any intervention arm. During the pre-study training session on the use of CGM, the CGM receiver may be masked to the study participant.

Data from the study CGM system will be downloaded periodically at least every four weeks during each intervention by the participant.

12.1.3 Insulin Pump Data

Data from the study insulin pump will be downloaded periodically during each intervention by the participant.

12.2 Questionnaires and Interviews

12.2.1 Questionnaires

Psychosocial data will be collected using a mixed methods approach. Quantitative data on health-related quality of life will be assessed using validated questionnaires. Participants/guardians will complete the questionnaires at screening and at the end of the study intervention. Additionally, feedback questionnaires on closed loop specific experience will be distributed to participants/guardians who had been randomised to the closed loop intervention arm. All results will be evaluated at the end of the study.

12.2.2 Qualitative Interview

A subset of participants randomized to a closed loop system will be interviewed at baseline (post-randomization) to enable their historical diabetes management practices, everyday work and family lives, and their initial expectations of using this technology to be captured and explored in-depth. The same participants will be followed-up 3 months later to look at whether, in what ways, and why, use of a closed loop system has impacted on their diabetes self-management practices, their attitudes towards hypoglycaemia; and, their work and family lives. These follow-up interviews will also explore how participants think the technology could be refined and improved in light of their

experiences of using it. A subset of family members will be interviewed at 3 months to capture the benefits of using a closed loop system from their perspectives, including how this technology has impacted on their own lives and on their role in supporting diabetes management practices. A family member recruitment pack will be given to participants/guardians at Visit 8 to pass onto a partner/adult family member in order to recruit the subset of family members for the interviews at 3 months. The family member recruitment pack can also be mailed or emailed after Visit 8 to participants/guardians.

Approximately 25 people with diabetes will be interviewed. This sample size will be large enough for a full range of issues relating to use of closed loop systems to be identified and explored in-depth and for data saturation to occur (i.e. for no new findings to emerge from any new data collected). If possible, participants will be purposively sampled so there is diversity in the final sample in terms of age, gender, occupation/education and geographical location. Approximately 20 family members will be interviewed.

Interviews will be informed by topic guides developed in light of literature reviews, initial research questions, inputs from the trial team and lay/patient advisors, and revised in light of emerging findings (see above). UK based interviews will take place at a time and location chosen by participants (most likely their own homes) and possibly by phone; US interviews will need to be undertaken by telephone. Interviews will be digitally recorded with consent and will average an hour.

To maximise rigour two experienced qualitative researchers will be involved in data analysis. A thematic analysis will be undertaken by these two individuals who will independently review all data before attending regular meetings to compare their interpretations and reach agreement on recurrent themes and findings. Each individual's baseline and three month interview will be compared, and attention paid to any continuities and changes in their attitudes, experiences and use of closed loop systems over time, and the reasons for these. Participants' accounts will also be cross-compared, enabling the identification of overarching themes which cut across different people's experiences. A final coding frame, reflecting the initial research questions and emergent themes, will be developed once all data have been reviewed and consensus reached on key themes and findings. NVivo9, a qualitative software package, will be used to facilitate data coding/retrieval.

12.3 Laboratory Methods

12.3.1 Screening Sample

Renal, liver and thyroid function and anti-transglutaminase antibodies with IgA levels (to exclude diagnosis of coeliac disease) and full blood count will be measured locally if not done within the previous 3 months.

12.3.2 C-peptide and Glucose

Random blood sample for the measurement of C-peptide with simultaneous exclusion of biochemical hypoglycaemia (blood glucose <4.0 mmol/l (72mg/dl)) by laboratory glucose analysis on a sample at the same time point, will be taken at screening.

Plasma C-peptide will be measured at a local laboratory.

12.3.3 HbA1c

Blood samples for the measurement of HbA1c levels will be taken at three different time points: screening, beginning¹ and end² of study intervention. An additional HbA1c sample will be taken at the beginning and end of study intervention for storage purposes.

Screening HbA1c will be measured locally. HbA1c taken at beginning and end of study intervention will be measured at a central laboratory in each country using an International Federation of Clinical Chemistry and Laboratory Medicine (IFCC) aligned method. HbA1c testing must follow National Glycohemoglobin Standardization Program (NGSP) standards.

12.4 Total Blood Loss

The total blood loss will be approximately 35 ml.

¹ An extra blood sample will be taken and frozen, to be stored as a spare HbA1c sample

² An extra blood sample will be taken and frozen, to be stored as a spare HbA1c sample

13 Study Materials and Products

13.1 Insulin

U-100 rapid acting insulin analogue will be used in the insulin pumps. This includes either Aspart (Novorapid; Novo Nordisk, Bagsvaerd, Denmark) or Lispro (Humalog; Eli Lilly, Indianapolis, USA) but not Glulisine (Apidra; Sanofi-Aventis, Paris, France)

13.2 Insulin Pump with Pump Suspend Feature

During day and night automated closed loop glucose control combined with threshold based pump interruption, the next generation Medtronic subcutaneous insulin infusion pump Medtronic 640G (Medtronic Minimed, Northridge, CA, USA) will be used. Threshold-suspend feature will be initially set to suspend insulin delivery at sensor glucose values of 3.9 mmol/l (70 mg/dl) or less, after which the setting could range from 2.8 to 5.0 mmol/l (50 mg/dl to 90 mg/dl).

13.3 Insulin Pump used during Run-in and Control Intervention

During sensor augmented insulin pump therapy, similar insulin pump device will be used (Medtronic 640G) but pump suspend feature will be turned off.

During run-in and to download insulin and sensor data during the interventional and control periods, Medtronic CareLink® Therapy Management Software or similar will be used.

13.4 Continuous Subcutaneous Glucose Monitor

The next generation Medtronic Enlite 3 family real-time sensor with Enliteserter (Medtronic Minimed, Northridge, CA, USA) will be used in the study. The sensor will be calibrated according to manufacturer's instructions with additional calibration checks in the morning and evening.

13.5 Carelink USB link

The Medtronic CareLink™ USB is indicated for use commercially by patients at home and for clinicians in a medical office setting as a means of facilitating communication between Medtronic diabetes therapy management devices that use Paradigm-compatible RF telemetry and a personal computer that uses data management application software. The CareLink USB device will enable data from study insulin pumps to be uploaded to CareLink Clinical.

13.6 Bayer CONTOUR™ Next Link Blood Glucose Meter

A Bayer Contour Next Link RF enabled BG Meter (Study Meter) will be provided to study participants for use with the study pumps. The meter measures a subject's capillary blood glucose level, which is then used to calibrate the pump. The study pumps use the calibration point in the real-time algorithm which calculates the sensor glucose values that are displayed to the subject.

13.7 Computer-Based Algorithm

The Cambridge closed loop controller has been used safely and effectively in the closed loop studies in both children and adults with T1D (study REC Ref. 06/Q0108/350, REC Ref. 07/H0306/116, REC Ref. 08/H0304/75, REC Ref. 08/H0308/297, REC Ref. 09/H0306/44, REC Ref. 10/H0304/87, REC Ref. 12/EE/0155, REC Ref. 12/EE/0034, and REC Ref. 12/EE/0424).

14 Data Analysis

14.1 Primary Analysis

The primary analysis will evaluate between group difference in the time (midnight to midnight) spent in the target glucose range from 3.9 to 10 mmol/l (70 to 180mg/dl) based on CGM glucose levels during the 12 week free living phase.

A 5% significance level will be used to declare statistical significance for the primary outcome comparison.

The primary analysis will follow the intention-to-treat principle. It will include all randomized subjects, the data from whom will be analysed in the group to which the subjects were assigned through randomisation regardless of the actual treatment received. Data will not be truncated due to protocol deviations.

Mean (SD) for % time spent in the target range will be tabulated by treatment group. A linear model will be used to compare the difference between the two intervention arms, while adjusting for baseline % time spent in the target glucose range and random site effect. A 95% confidence interval will be reported for the difference between the treatment groups based on the linear model. Normality of the residuals will be assessed. If the residuals have highly skewed distribution, then ranked normal score transformation of outcome data will be applied in the regression model. However, previous experience suggests that % time in target glucose range will follow an approximately normal distribution. A detailed analysis plan will be provided separately.

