7.4 Randomisation

Eligible subjects will be randomised using central randomisation software to the use of day and night closed loop combined with pump suspend feature or to sensor augmented insulin pump therapy. The randomisation will be stratified at each centre by HbA1c groups [equal proportion of below and above 8.5% (69mmol/mol)]. Each site will recruit only in one of the two age groups [youth (6 to 21 years) or adults (22 years and older)].

8 Methods under Investigation

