14.5 Subgroup Analysis

No subgroups were considered during the power calculations. Interpretation of any subgroup analyses will depend on whether the overall analysis demonstrates a significant treatment group difference. In the absence of such an overall difference and if performed, the following subgroup analyses will be interpreted with caution: (1) age (6 to 12 years, 13 to 21 years, 22 years and older), (2) gender, (3) race-ethnicity, (4) clinical centre, and (5) baseline HbA1c (<8.5% and ≥8.5%).

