14.10 Sample Size and Power Calculations

Based on our previous day-and-night closed loop studies and a conservative estimate of 10 percentage points improvement in time when glucose is in target glucose range with a SD of 14.5 percentage points, 76 subjects are required to achieve 85% power and an alpha level of 0.05 (two-tailed). 84 are planned to be randomised to allow for dropouts. It is expected that 95 or more subjects will be recruited; recruitment will continue until it is anticipated that a sufficient number have been enrolled to meet the randomisation goal. Randomisation target may be exceeded since all of the subjects who have initiated the run-in phase will be permitted to continue into the intervention.

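### The primary model leaves out the HbA1c stratum used at randomisation, so its confidence interval may be slightly too wide

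*Protocol*

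**What the plan says.** Protocol section 7.4: "The randomisation will be stratified at each centre by HbA1c groups", with the cut at 8.5%. Inclusion criterion 6 (section 7.2) ties the same cut to the screening HbA1c from the local laboratory.

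Protocol section 14.1 names the covariates of the primary linear model: the arms are compared "while adjusting for baseline % time spent in the target glucose range and random site effect". It adds: "A 95% confidence interval will be reported for the difference between the treatment groups based on the linear model". The HbA1c group is not in the list. The section also says that a detailed analysis plan will follow separately.

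Section 14.2 uses similar linear models for the secondary glycaemic metrics. In the analysis section, the 8.5% cut returns only in section 14.5, as the subgroup factor "baseline HbA1c (<8.5% and ≥8.5"%.

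**The concern.** The design has two randomisation factors, centre and HbA1c group. One is in the primary model and the other is not.

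Balancing the arms on a factor that predicts the outcome removes that factor's contribution to the chance difference between arms, so the treatment estimate varies less from trial to trial. A model without the factor leaves its contribution in the residual variance. The reported standard error is then larger than the true variability of the estimate. The interval is too wide and the test is conservative. At stake is some precision that the design has already paid for.

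**Working it through.** **1. The plan's own figure.** Section 14.10 gives "a conservative estimate of 10 percentage points improvement in time when glucose is in target glucose range" "with a SD of 14.5 percentage points", two-sided alpha 0.05, and states that "76 subjects are required to achieve 85% power". Assuming 1:1 allocation, n per arm = 2 × (1.960 + 1.036)² × 14.5² / 10² = 37.75, rounded up to 38, or 76 in total. The figure reproduces under the normal approximation. (The exact t-test gives 84.3% power at 38 per arm and needs 78 for 85%.) The calculation takes no credit for any covariate, so it does not depend on whether the stratum is in the model.

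**2. Half-width without the stratum.** Read 14.5 as the residual SD after baseline time in range and site (an assumption), with 84 subjects, 42 per arm:
- SE = 14.5 × √(2/42) = 3.164
- half-width = 1.96 × 3.164 = 6.202 points

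**3. Half-width with the stratum.** Let R² be the share of that residual variance which the stratum explains. The half-width becomes 6.202 × √(1 − R²), so the interval without the stratum is wider by the factor 1/√(1 − R²). The protocol gives no R², so a range is shown:

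| Assumed partial R² | Half-width with stratum | Excess width without it | Power at 84 with stratum |
|---|---|---|---|
| 0% | 6.202 | 0% | 88.5% |
| 2% | 6.139 | 1.0% | 89.1% |
| 5% | 6.045 | 2.6% | 90.0% |
| 10% | 5.883 | 5.4% | 91.5% |
| 20% | 5.547 | 11.8% | 94.2% |

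Power with the stratum is Φ(10 / (3.164 × √(1 − R²)) − 1.96).

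**4. What these R² values mean.** For a stratum that splits the sample in half, a partial R² needs an adjusted difference between the HbA1c groups of at least 2 × 14.5 × √R². That is 4.1 points of time in range at 2%, 6.5 at 5%, 9.2 at 10% and 13.0 at 20%, all after adjustment for baseline time in range and site.

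**5. Power without the stratum.** With the strata balanced, the estimate varies by only √(1 − R²) of the reported SE. Power without the stratum is therefore Φ((10/3.164 − 1.96) / √(1 − R²)): 89.1% at R² 5% and 89.7% at 10%. Against 90.0% and 91.5% in the table, including the stratum gains about 1 and 2 percentage points.

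**6. Simulation.** The set-up was 84 subjects, six equal sites, permuted blocks within site and HbA1c stratum, and 3,000 runs per scenario. Block size 2 and a fixed rather than random site effect were assumed. The ratio of interval widths (stratum omitted to included) was 0.997 to 0.998 at R² 0, about 1.01 at 2%, 1.03 at 5%, 1.06 at 10% and 1.13 at 20%. It hardly changed with the assumed correlation of HbA1c with baseline time in range (0.4 to 0.8).

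At R² 20% without the stratum, the mean model SE was about 3.22 against a true SD of 2.90 to 3.05, and type I error was 2.9 to 4.0%. Adding the stratum brought it back to about 5%. At R² 0 to 5%, the omitted-stratum type I error showed no clear departure from 5% given the simulation error (one standard error is about 0.4 percentage points).

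**The case against.** **The balance is not ignored.** Site is in the model, and so is continuous baseline time in range, a closely related measure of pre-treatment glycaemia. HbA1c is also confined to 7.5 to 10% by inclusion criterion 6, so the stratum splits a narrow range. This stands. A reader might infer that the interval is certainly too wide, but the documents support only the conditional statement. Nor do they support a large effect. A remaining stratum effect of 0.8 SD, for example, would be 0.8 × 14.5 = 11.6 points, more than the 10-point treatment effect for which the trial is powered.

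**Planned power is not lost.** This also stands. The loss is only against a slightly better model.

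**Secondary outcomes.** A reader might infer that every secondary comparison loses precision. That is not shown. Section 14.2 speaks only of similar models, and section 14.7 adjusts each score for its own baseline. If the HbA1c model does likewise, the dichotomised screening value should add little.

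**Subgroup.** A reader might also infer that the HbA1c subgroup in section 14.5 differs from the randomisation stratum. Section 12.3.3 offers two candidates: screening (local laboratory) and start of intervention (central laboratory, drawn at Visit 5 after randomisation). Section 14.5 does not say which is meant, so a mismatch is possible but not established. A value drawn before study treatment begins is in any case a usable baseline.

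**The separate analysis plan may add the stratum.** It may. But the protocol itself fixes the covariate list, and that list leaves out a randomisation factor without a reason. The core point therefore survives.

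**Conclusion.** The mismatch is real and its consequence is small. The stated primary model omits one of the two factors on which allocation is balanced. As far as that factor predicts time in range beyond baseline time in range and site, the reported standard error is conservative. The excess interval width is about 0 to 3% at an assumed partial R² of 0 to 5% and about 5% at 10%. It would reach about 12% only at 20%, which needs an adjusted difference between HbA1c groups of at least 13 points.

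These sizes rest on the assumed R², on reading 14.5 as the residual SD, and on 42 analysed per arm. The error is on the safe side, and it threatens neither the validity of the primary comparison nor its planned power.

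**What to change.** In section 14.1, add the HbA1c stratum as used at randomisation (below or above 8.5%), or continuous screening HbA1c, as a fixed covariate, or else state why it is left out. Make the same change in the section 14.2 models that follow the primary model. Optionally, state in section 14.5 that the HbA1c subgroup is the same randomisation stratum.

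The cost is one line of text and one degree of freedom. If the stratum proves uninformative, the interval widens by only 0.2 to 0.3% (simulated width ratio 0.997 to 0.998).
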